Study Objective(s)	
 1. To determine whether STX209 produces a significant change in MEG target parameters compared to baseline as well as compared to placebo treatment. Secondly, to determine if the magnitude of such change is influenced by STX209 dose: 0 mg (placebo) versus 15mg versus 30 mg. 2. To determine whether STX209 leads to a significant change in MRS-obtained auditory cortex GABA levels compared with placebo treatment. Secondly, to determine whether the magnitude of the GABA change is influenced by STX209 dose level. 3. To determine if dose-dependent changes in MEG target parameters are correlated to dose-dependent changes in MRS target parameters in auditory cortex.
Test Article(s) (If Applicable)	STX209 (Arbaclofen), a GABA-B agonist and a matching placebo. The active compound is made available to this project by the Clinical Research Associates, LLC (CRA).

Study Design	A randomized acute dose-response design will be employed with a total study duration of 3 weeks. At each visit, baseline MEG will be obtained followed by acute single-dose drug/placebo administration, followed 60 minutes later by repeat MEG. Each participant will receive a single dose of placebo in random order and a single dose of STX209 from smallest to largest (15mg and 30mg). MRI and MRS will be performed immediately following MEG to provide an anatomic basis for source localization as well as to assess acute effects of STX209 administration on MRS estimates of GABA and glutamate.
Number Of Subjects	This is a single site study. 40 male subjects with ASD will be recruited in order to get 38 evaluable subjects.
Study Duration	Subjects will be examined at three separate sessions, at each session receiving in random order a single-dose of placebo, and from smallest to largest a single-dose of STX209 (15mg and 30mg). Each subject's participation will last approximately 4 weeks although participation could be extended up to six or eight weeks if subjects are unable to come four consecutive weeks in a row. The entire study is expected to last one year.
Study Phases	
Screening	Screening for eligibility, obtaining consent, and cognitive and clinical symptom assessments
MEG Assessments	Over a period of 3 visits (at least 1 week apart), baseline MEG exam and then MEG/MRS assessment of STX209 at 15mg and 30mg doses or a single placebo.

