3.1.3 MEG Assessments: Visits 1-3

On the next three visits (scheduled to occur within a range of 3-12 months of the clinical/behavioral testing) MEG, MRI, and MRS measures will be collected at each study visit in the Dept. of Radiology. MEG testing will last approximately 3 hours (pre- and post STX209 scanning, with 1 hour period between baseline and post-STX209 administration) and MRI will take approximately an additional 1 hour (after the post-MEG exam) For MRI, no sedation or contrast will be used.

Specifically, we will accept behavioral testing within a 6-12 month timeframe and will accept Blood Draw results and Physical Examination review within 3 months of the first imaging visit. For cases where there has been a 3 month or more lag between screening visit and imaging visit, the Blood Draw and Physical Exam will be repeated to ensure safety and adequate monitoring (as noted above, in cases where subject is unable to do a blood draw on the day of the screening visit due to anxiety/fear/discomfort if no medical risk factors are identified during medical history review, we will either accept BUN and Creatinine results from an outside source within 3 months of first imaging visit or attempt to do the blood draw on the day of the imaging visit.).

Upon arrival, MEG data will be collected to obtain baseline measures. At the conclusion of the baseline MEG scan, participants will be randomly administered a single dose of placebo and in order of increasing order a single-dose of STX209 (15mg and 30mg). Based on advice from Seaside Therapeutics, given the time course of plasma STX209 levels, the MEG examination will be repeated 60 minutes after drug administration. Following the MEG exam, subjects will obtain a 3T MRI to obtain an anatomic 3D image (MP-RAGE) and bilateral STG GABA and glutamate measures (MEGAPRESS MRS). Subjects will return for their imaging study visits no less than four days or more than 14 days to repeat the MEG and MRI and MRS exams, each time with a different drug/placebo dose.

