4.3 MEG and MRI/MRS Assessment Phase: Visit 1-3

On the next three visits (scheduled to occur within 3 months of the physical examination and within 12 months of clinical/behavioral testing) MEG, MRI and MRS measures will be collected at each study visit. Upon arrival, vital signs will be collected. Then pre-drug MEG data will be collected to obtain baseline measures. At the conclusion of the baseline MEG scan, participants will be randomly administered a single-dose of Placebo and single-dose of STX209 in order of smallest to largest dose (15mg, 30mg) (see Section 3.2). Based on advice from Clinical Research Associates, LLC (CRA), given the time course of plasma STX209 levels, the MEG examination will be repeated 60 minutes after drug administration. Following the MEG exam, subjects will obtain a 3T MRI to obtain an anatomic 3D image (MP-RAGE) and bilateral STG GABA and glutamate measures (MEGAPRESS MRS). At the end of the scanning visit AE will be assessed via the SMURF form. Subjects will return for their imaging visit no less than four days or more than 14 days to repeat the MEG, MRI and MRS exams, each time with a different drug/placebo dose.

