Screen for Eligibility Criteria	10 min
Pre-Intake Questionnaire (Demographics)	20 min
Subtotal:	75 min
Screening Visit:	
Medical, Diagnostic, and Neuropsychological Assessments	
Procedures administered to Parent/Legal Guardian (at the same time as child testing)	
Intervention History Form	15 min
Medical History Form	30 min
Child Behavior Checklist (CBCL) (if applicable)	20 min
Social Communication Questionnaire (SCQ) (if applicable)	5 min
Social Responsive Scale-II (SRS-II) (if applicable)	10 min
Vineland Adaptive Behavior Scale (if applicable)	20 min
Autism Diagnostic Observational Scale (ADOS-2) (if applicable)	60 min
Subtotal:	2 hours and 40 min
Procedures individually administered to children:	
Physical Examination	15 min
Blood Draw	10 min
Vital Signs	10 min
Clinical Evaluation of Language Fundamentals (CELF –IV)	
(if applicable)	60 min
Wechsler Abbreviated Scale of Intelligence (WASI-II) (if applicable)	60 min
Baseline SMURF	20 min
MRI Mock Scan (optional)	30 min
Subtotal:	3 hours and 25 min

* Diagnostic and neuropsychological testing will not occur if testing scores are available (less than 12 months prior to screening visit) for re-recruited participants (data from tests will only be used if subjects who previously participated in one of our research studies, agreed to share their data on future studies). Only the medical assessments (e.g., vital signs, physical exam, medical history, intervention history form, and blood draw) will be completed for re-recruited participants at screening visit. Therefore, the screening visit will last approximately 80 minutes for re-recruited participants.

MEG Assessment 1: Visit 1

Procedures individually administered to participants at Visit 1	
Autism Diagnostic Interview – Revised (ADI-R) (if applicable)	180min
Vital Signs	10 min

Pre Drug MEG Scan	45 min
MRI Scan	30 min
Administration of STX209/Placebo	< 10 min
MRI Scan continued	30 min
Break	30-60 min
Post Drug MEG Scan	45 min
Adverse Event Assessment (SMURF)	20 min
Subtotal:	4 hours and 50 min

MEG Assessment 2: Visit2

Procedures individually administered to participants at Visit 2	
Vital Signs	10 min
Pre Drug MEG Scan	45 min
MRI Scan	30 min
Administration of STX209/Placebo	< 10 min
MRI Scan continued	30 min
Break	30-60 min
Post Drug MEG Scan	45 min
Adverse Event Assessment (SMURF)	20 min
Subtotal:	4 hours and 10 min

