8.4.2 Risk Assessment

As with any study of a novel therapeutic, there are at least minor risks associated for participants receiving the study drug. Adverse effects associated with STX209 in human trials have included sedation, agitation, irritability, psychomotor hyperactivity, headache, fatigue, diarrhea, and vomiting. However, rates of adverse effects and rates of withdrawal due to adverse effects were lower than for racemic baclofen, which is already in clinical use. Additional adverse effects reported with use of racemic baclofen, and rarely (< 1%) occurring in previous studies of STX209, included neuromuscular weakness, worsening of seizures in a known seizure disorder, and mild hallucinations. In addition, a time commitment of approximately 12.5 hours is expected in total for the four visits, which may be inconvenient. Some of the questions the children will be asked during the WASI testing may be hard for them (e.g., challenging problem solving, block design), which may cause some nervousness. The examiner will make every effort to reduce frustration and provide breaks when needed. In the second session, children may find lying on the MEG bed slightly uncomfortable and/or feel mildly "closed-in" (or claustrophobic) -with his/her head inside the MEG machine. We will make every effort to reduce any discomfort including pillows, blankets and the availability of video movies (during times when visual stimuli are not presented). There are no known medical risks associated with magnetic resonance imaging (MRI). However, children may experience mild discomfort or feelings of claustrophobia. Each child will be provided with a squeeze ball alarm as well as voice intercom to indicate that they would like to stop the MRI scan. Ear plugs will be provided to reduce the noise of the MRI scan. A video movie will be presented during MRI to make the experience more comfortable

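### The 5.2.1 visit timetables place the MRI around dosing, between the two MEG recordings, while the synopsis, 3.1.3 and 4.3 place it after the post-dose MEG; the orders must be reconciled because the planned MEG contrasts and the GABA endpoint depend on which is followed

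*Combined protocol and SAP*

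**What the plan says.** **Order in 5.2.1.** The timetables for Visits 1, 2 and 3 share one sequence: vital signs 10 min; "Pre Drug MEG Scan" 45 min; MRI 30 min; "Administration of STX209/Placebo" under 10 min; "MRI Scan continued" 30 min; break 30-60 min; post-dose MEG 45 min; then safety assessments (plus a physical examination at Visit 3). No MRI follows the post-dose MEG. The section introduces its list as showing when each measure is given, but also calls it a summary, with approximate times.

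**Order elsewhere.**
- Synopsis, Study Design: "MRI and MRS will be performed immediately following MEG". The sentence comes after the repeat MEG and gives acute drug effects on GABA and glutamate as one purpose.
- 3.1.3: "MRI will take approximately an additional 1 hour (after the post-MEG exam").
- 4.3: "the MEG examination will be repeated 60 minutes after drug administration", with the MRI following that MEG. The note to Table 1 also gives 60 minutes.

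No section states a tolerance for the 60 minutes.

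**What rests on it.** The primary endpoints (5.4) are changes from baseline to STX209 in auditory latencies and gamma measures. The two a priori contrasts (5.6, 5.6.2) compare baseline with the average of the active doses, and baseline with 15 mg and 30 mg. The ANOVA in 5.6 covers placebo, and Objective 1 (2.1) names a placebo comparison, but neither contrast includes placebo. The GABA endpoint (5.5) is a change from baseline; Objective 2 (2.1) compares GABA with placebo.

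**The concern.** A coordinator working from 5.2.1 and one working from 4.3 would run different sessions. Two things are at stake.

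- **MEG.** If the timetable is followed, the post-dose auditory recording comes after two MRI slots that the pre-dose recording did not. Noise, confinement, fatigue or elapsed time could move auditory latency or gamma without any drug effect. A contrast of baseline with active dose cannot separate such a shift from the drug.
- **MRS.** If the timetable is followed, GABA is measured before dosing or very soon after it. If the text is followed, it is measured after the post-dose MEG. A change-from-baseline endpoint and a comparison with placebo both need a stated acquisition time relative to dose.

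**Working it through.** **1. Check the reading of the timetable rows.** Visit 2 is stated as "4 hours and 10 min", or 250 min. Summing the rows with 10 min for dosing and a 60-min break: 10 + 45 + 30 + 10 + 30 + 60 + 45 + 20 = 250 min. This matches. With a 30-min break it is 220 min.

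The other totals do not reproduce. Visit 1 sums to 3 h 30 - 4 h 10 without the ADI-R, or 6 h 30 - 7 h 10 with it, against 4 h 50 stated. Visit 3 sums to 3 h 45 - 4 h 25, against 4 h 40 stated. The Visit 2 total does not settle the order, because the text order also gives 10 + 45 + 10 + 60 + 45 + 60 + 20 = 250 min.

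**2. Compare the two orders.**

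| Quantity | 5.2.1 timetable | 3.1.3 / 4.3 |
|---|---|---|
| MRI slots between the MEG recordings | 30 + 30 = 60 min | 0 |
| End of pre-dose MEG to start of post-dose MEG | 30 + (0 to 10) + 30 + (30 to 60) = 90-130 min | about 60 min plus dosing |
| End of dosing to post-dose MEG | 30 + (30 to 60) = 60-90 min | 60 min |
| Start of dosing step to post-dose MEG | up to 10 + 30 + 60 = 100 min | 60 min |
| MRS | before dosing, or in roughly the first 30 min after it | after the post-dose MEG, so from about 60 + 45 = 105 min (45-min MEG slot from 5.2.1) |

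Section 1.3.1.2 gives a Tmax of about 60 min. Under the timetable, all MRS would therefore precede the plasma peak.

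**3. How a non-drug shift enters the planned contrasts.** Let *s* be a pre-to-post shift common to all visits and *d* the drug effect.
- Baseline versus active estimates *d* + *s*.
- Active change minus placebo change estimates (*d* + *s*) - *s* = *d*.
- The difference between 15 mg and 30 mg is also free of *s*.

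**4. Illustration of scale.** The values of *s* are assumptions, because the documents give none. From 5.7: n = 36, alpha 0.05 (taken as two-sided), expected M100 change 2.5 ms. The SD is described only as similar in size, which could mean 2.5 or 5 ms. For a one-sample t test with 35 df, the noncentrality is *s*/SD × √36 = 6*s*/SD.

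First, the plan's own power of 0.80 for a 2.5 ms change: SD 2.5 gives above 0.999, SD 5 gives 0.83, and 0.80 needs SD of about 5.2. The point does not rest on this figure.

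Probability that baseline versus active is significant with *d* = 0:

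| *s* | SD 5 ms | SD 2.5 ms |
|---|---|---|
| 0 | 0.05 | 0.05 |
| 0.5 ms | 0.09 | 0.22 |
| 1.0 ms | 0.22 | 0.65 |
| 1.5 ms | 0.42 | 0.94 |

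**5. Effect of the variable break.** Assume a one-compartment oral model, C(t) ∝ exp(-ke·t) - exp(-ka·t), with ke = ln 2 / half-life, half-life 5.04-5.85 h (1.3.1.2), and ka chosen so that Tmax is 1 h (ka 3.32-3.51 per hour). Plasma level relative to 60 min is then about 0.97 at 90 min and 0.95 at 100 min, a difference of about 3-5%.

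**The case against.** The strongest reply is that 5.2.1 is a loose run sheet: it calls itself a summary, gives approximate times, and two of its three totals do not add up. The synopsis, 3.1.3 and 4.3 agree on MRI after the post-dose MEG. Each version also applies one order at every visit, placebo included, so a common shift cancels in the placebo comparison named in Objective 1. All of this stands. It does not remove the contradiction: the split scan appears at all three visits, so it is hard to read as a slip. Nor does it protect the a priori contrasts, which omit placebo.

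Three stronger readings are tempting, and the documents do not support them.
- A reader might infer that the primary change score is in fact contaminated by scanner noise. That holds only if the timetable is the schedule used, which the documents do not establish. They give no size for such an effect, and 8.4.2 says "Ear plugs will be provided to reduce the noise of the MRI scan". The 60 minutes are scan slots; acoustic exposure time is not given.
- A reader might convert a shift in hearing threshold into milliseconds of M100. No slope and no threshold shift are documented, and the protocol does not say whether sensation level is re-measured before each recording.
- A reader might infer that the 30-60 minute break confounds dose with time since dose. Nothing links break length to dose. Variable timing would mainly add variance, and the modelled plasma difference is small, although time course at the effect site is not given.

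**Conclusion.** The contradiction is certain and needs correcting. Its consequences are conditional on the 5.2.1 timetable being followed. In that case, 60 min of MRI slots separate the two recordings, any non-drug shift passes undiluted into both baseline-versus-active contrasts, and MRS has no acquisition time consistent with the text. On the assumed shifts in the working, even 1 ms would raise the chance of a false positive from 0.05 to 0.22 (SD 5 ms) or 0.65 (SD 2.5 ms). These figures show sensitivity; they do not estimate a scanner effect. If the text order is followed at every visit, no MRI falls between the recordings, but the contrasts would still carry any other pre-to-post drift because they omit placebo.

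**What to change.** - Reconcile 5.2.1 with the synopsis, 3.1.3 and 4.3 so that one order applies at all three visits, with no MRI between the two MEG recordings unless a pre-dose MRS is intended for the change-from-baseline GABA endpoint in 5.5. If it is intended, say so, and state when each MRS is acquired.
- State one dose-to-MEG interval with a tolerance. Record actual dose-to-MEG and dose-to-MRS times.
- Test the MEG change scores as active minus placebo, so that common non-drug shifts cancel.
- Reconcile the stimulus level in 5.1.6, which gives 40 dB in the general description and 45 dB for the tone and steady-state tasks.
- Correct the Visit 1 and Visit 3 totals.

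**Cost.** The schedule changes are wording only. The waiting period would no longer be used for MRI, and a visit could run up to 250 - 220 = 30 min longer than the timetable's shortest version. The placebo-referenced contrast needs its own power statement. If change scores have equal variance σ² and correlation ρ between visits (an assumption; neither is given), the averaged active change has variance σ²(1 + ρ)/2, and its difference from placebo has variance σ²[(1 + ρ)/2 + 1 - 2ρ] = 1.5σ²(1 - ρ). That is three times as large at ρ = 0 and equal at ρ = 0.5.

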5.3 Safety Evaluation

There were no significant safety or tolerability concerns from previous studies with STX209. AEs reported that were higher in frequency during the STX209 period of the double-blind study, or with incidence >15% in the open-label study included: headache, sedation, fatigue, increased agitation, increased irritability, vomiting, and psychomotor hyperactivity. Other AEs with incidence >5% of subjects included: diarrhea, insomnia, aggression, disturbance in attention, nasopharyngitis, abdominal pain, cough, decreased appetite, pharyngitis streptococcal, self-injurious behavior, asymptomatic decreased heart rate, and upper respiratory tract infection.

Based upon information on the action of STX209 (published reports and information from Seaside Therapeutics), several procedures will be followed to ensure subject safety. First, since STX209 is excreted renally, subjects will be excluded if laboratory tests indicate abnormal renal function (i.e., for their age, abnormal BUN and Creatinine levels) at the Screening Visit (To minimize harm to the subject, in cases where subject is unable to do a blood draw on the day of the screening visit due to anxiety/fear/discomfort, if no medical risk factors are identified during medical history review, we

will either accept BUN and Creatinine results from an outside source within 3 months of the first imaging visit or attempt to do the blood draw on the day of the imaging visit.). Second, since hypotension is a potential risk with STX209, blood pressure will be documented at each visit. Individuals with a significant change in blood pressure (determined by the medical monitor or PI) following administration of STX209 will be discontinued from the study visit if it is a Minor Adverse Event or will be discontinued from the entire study if it is a Severe Adverse Event.

Subject safety will be monitored by adverse events, blood draw, vital signs, and physical examination findings and concomitant medication usage.

STATISTICAL CONSIDERATIONS

5.4 Primary Endpoint

The primary endpoints are (1) change from baseline to STX209 administration in left and right superior temporal gyrus auditory M50, M100 and MMF latencies, and (2) change from baseline to STX209 administration in left and right superior temporal gyrus auditory gamma total power and phase-locking measures (examined pre- and post-stimulus).

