 - 2) Binaurally presented 300 and 500Hz 300ms duration sinusoidal tone (45dB SL), using the task reported in Roberts et al. (2010). (2 minutes)
 - 3) Auditory 40 Hz steady-state task, presenting 200 trials of 40 Hz amplitude modulated (AM) sinusoidal tones (500 ms long, 45 dB SL) with a jittered 1.5 sec inter-stimulus interval. (7 minutes)
 - 4) Oddball auditory task with interleaved /a/ and /u/ vowel stimuli as in Roberts et al. (2011). (12 minutes)
- 2) **MRI/MRS** Magnetic resonance imaging will then be performed using a 3T Siemens Trio MR scanner in the Department of Radiology at Children's Hospital of Philadelphia. This state of the art equipment is equipped with multi-channel RF capabilities (allowing parallel imaging

(Pruessmann et al. [17]). A mock scanner (Nordic Neurolabs) is available for subject conditioning and paradigm practicing. Sequences will include:

- 1) localizer scouts (3-plane)
- 2) inversion-recovery prepped 3D gradient recalled echo imaging sequences for anatomic visualization (high resolution 256x256x160 matrix, isotropic 1mm resolution)
- 3) MEGAPRESS single voxel edited magnetic resonance spectroscopy sequence and analysis, as provided by Siemens Medical Solutions

All of the above MRI sequences are FDA-approved with the exception of the MEGAPRESS. The MEGAPRESS sequence was recently developed and measures brain chemistry (for example GABA). The MEGAPRESS sequence will take approximately 20 minutes and will be obtained for all participants.

The MEGAPRESS MR pulse sequence is not specifically approved by the FDA. It was obtained from Siemens Medical Solutions as a Works-in-progress (WIP #529). The conditions of use of this WIP is that it is not to be used for clinical interpretation and that it should be used under IRB-approved protocols. Technically, it is a very simple modification of the conventional approved MR spectroscopy pulse sequence, in which a mathematical subtraction allows resolution of the previously obscured GABA resonance (by cancelling the overlapping Creatine resonance). It is extremely widely used in research studies worldwide. The conditions of use of a WIP is that it is not to be used for clinical interpretation and that it should be used under IRB approved protocols.

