5.2 Efficacy Evaluations

The measures used to assess efficacy of STX209 are:

1. Change from baseline to STX209 administration in left and right superior temporal gyrus auditory M50, M100 and MMF latencies. To measure M50 (40-90ms) and M100 (90-180ms) STG latency (and amplitude), pre-stimulus baseline activity will be subtracted, and right and left M50 and M100 superior temporal gyrus latency and amplitude calculated from the largest amplitude point in the scoring windows using in-house MatLab software. These extended latency ranges allow for M50 and M100 latencies observed in younger children and for low frequency (e.g. 300Hz) stimuli.
2. Change from baseline to STX209 administration in left and right superior temporal gyrus auditory gamma total power and phase-locking measures (examined pre- and post-stimulus). Calculation of single-trial phase/magnitude for right and left STG sources will use complex demodulation procedures[18] implemented in BESA 5.3™, using frequencies between 4 and 80Hz, in steps of 2Hz. Continuous data will be analyzed relative to the tone onset every 25ms, using +/-39.4ms and +/- 2.83Hz (FWHM parameters) of contiguous data at each step. For evoked activity, background activity at each frequency (average power -400 to -100ms) will be subtracted. In addition to evoked power, for each time-frequency bin, a measure of phase-locking referred to as inter-trial coherence (ITC) will be computed, according to $ITC = \text{abs} \left\{ \frac{1}{N} \sum_{k=1}^N e^{i\phi(k)} \right\}$, where N is the number of trials, and $\phi(k)$ is the phase of the signal in the k^{th} trial. ITC is a normalized measure with ITC=1 reflecting no phase variability and ITC=0 reflecting maximal phase variability across trials. The above time-frequency measures will be obtained for the pure-tone and steady-state tasks.

5.2.1 Diagnostic Tests, Scales, Measures, etc.

The following methods will be used to determine whether initial diagnostic criteria and inclusion/exclusion criteria are met, as well as to assess efficacy of intervention. They are listed with their timing of administration. The list provides an overview/summary of all measures given to child participants and their primary caregivers, including screening measures.

Screening - Contact Prior to Visits to CHOP	Approximate Time Demand
Parent/Legal Guardian	
Study description phone script	10 min
Collected by Phone:	
Verbal Consent for Phone Screening	5 min

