5.6.2 Efficacy Analysis

Our principal hypotheses relate to baseline to STX administration changes in the latency of the auditory M50, M100 and MMF responses, and gamma-band total power and inter-trial coherence (examined pre- and post-stimulus). To this end, for each dependent measure, ANOVAs with dose as a repeated measure will examine baseline versus post acute-dose changes (analyses showing no significant differences across time in baseline M50, M100, MMF and gamma measures will allow use of a single averaged baseline measure). Contrasts of *a priori* interest assess (1) a baseline versus post-acute dose change in the dependent measures averaging across STX209 15 and 30 mg, as well as (2) a change in dependent measures from baseline versus STX209 15 mg versus STX209 30 mg, with this test demonstrating an effect of dose. For the secondary endpoints, associations between MRS GABA/Cr ratios and the MEG dependent measures will be assessed using Pearson correlation analyses.

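### Pre-stimulus inter-trial coherence is listed as a primary endpoint, but by the protocol's own formula it sits at a chance floor before the tone and cannot show a drug effect on pre-stimulus synchrony

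*Combined protocol and SAP*

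**What the plan says.** Section 5.4 lists as its second primary endpoint the change from baseline in "left and right superior temporal gyrus auditory gamma total power and phase-locking measures (examined pre- and post-stimulus". Section 5.6.2 repeats this among the principal hypotheses and names the measure: "gamma-band total power and inter-trial coherence (examined pre- and post-stimulus". Section 5.2 and the efficacy list in the synopsis carry the same pre- and post-stimulus tag.

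Section 5.2 defines one phase-locking measure, ITC: the length of the average unit phase vector over N trials. The time reference is the tone: "Continuous data will be analyzed relative to the tone onset every 25ms". The scale is described as follows: "ITC is a normalized measure with ITC=1 reflecting no phase variability and ITC=0 reflecting maximal phase variability across trials". On scope it adds: "The above time-frequency measures will be obtained for the pure-tone and steady-state tasks". The same section subtracts mean power between -400 and -100 ms as background when it derives evoked power.

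Section 5.1.6 describes the steady-state task as "presenting 200 trials of 40 Hz amplitude modulated (AM) sinusoidal tones (500 ms long, 45 dB SL) with a jittered 1.5 sec inter-stimulus interval". For the pure-tone task it gives tone length (300 ms) and duration (2 minutes), but no interval, jitter or trial count.

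Other text is narrower. Section 5.6 and the statistical plan in the synopsis restrict the primary gamma analysis to post-stimulus activity. Section 5.7 gives power for post-stimulus gamma only. The abstract attaches synchrony to the auditory evoked response and lists only power for the resting state.

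**The concern.** ITC is defined by an event. If ongoing gamma has random phase when the tone arrives, averaging unit phase vectors over trials returns only what is left of a random walk. Its expected length depends on the number of trials, not on the strength or synchrony of the subject's gamma.

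If Sections 5.4 and 5.6.2 are followed as written, one stated primary measure carries no information about what it is named for. A null result could be taken to mean that STX209 leaves pre-stimulus synchrony unchanged, which would not have been tested. A positive result would be a chance finding, filter leakage, or a difference in usable trials. The risk of misreading is real because Section 1.3 cites both baseline and auditory-evoked gamma synchrony in mouse models. A reader could take pre-stimulus ITC as the human counterpart of the former.

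**Working it through.** The plan gives no expected value, effect size or power for pre-stimulus ITC, so there is no stated figure to reproduce. The gamma power of about 0.70 in Section 5.7 concerns post-stimulus activity only.

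**Inputs.** From the protocol: N = 200 trials, 500 ms tones and a jittered 1.5 s interval (5.1.6); 25 ms steps and ±39.4 ms FWHM (5.2); gamma band 30–50 Hz (synopsis rationale); analysed sample 36 (5.7). Assumed: jitter width, simulated signal-to-noise, and 50–100 pure-tone trials.

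**1. Chance floor.** For uniform random phase, E[ITC] ≈ sqrt(pi/(4N)) and SD ≈ sqrt((4 − pi)/(4N)).

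| N | Floor | SD |
|---|---|---|
| 200 | 0.0627 | 0.033 |
| 140 | 0.0749 | 0.039 |
| 100 | 0.0886 | 0.046 |
| 50 | 0.1253 | 0.066 |

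Simulation at N = 200 gave a mean of 0.0628, an SD of 0.033 and a 95th percentile of 0.122.

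**2. Does a drug-like change move it?** I simulated a 40 Hz signal with 200 trials, the previous onset 2.0 s earlier, a Gaussian window of 78.8 ms FWHM and jitter of ±100 ms.

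| Scenario | ITC, -400 to -100 ms | ITC at -25 ms | ITC at 150 ms |
|---|---|---|---|
| Base | 0.062 | 0.068 | 0.77 |
| Evoked response doubled | 0.063 | 0.078 | 0.95 |
| Background power doubled | 0.062 | 0.062 | 0.63 |
| No evoked response | 0.061 | 0.061 | 0.06 |

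The post-stimulus value responds and the pre-stimulus value stays at the floor. The small rise at -25 ms when the evoked response is doubled is the post-stimulus response leaking back through the filter.

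**3. Does this depend on the jitter?** Uniform jitter of ±W seconds retains |sin(2·pi·f·W)/(2·pi·f·W)| of any locking to the previous tone.

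- At ±50 ms it is zero at 30, 40 and 50 Hz.
- At ±10 ms it would be 0.51, 0.23 and 0.00 at those frequencies.
- At 40 Hz, widths such as ±12.5 or ±25 ms cancel exactly only because the full width is a whole number of 25 ms cycles.

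So an unstated jitter width does not settle the question alone. The silent gap does: with no jitter at all, the simulated values at -400 to -100 ms are 0.062–0.064. The stated 7-minute duration fits 200 × (0.5 + 1.5) s = 400 s = 6.7 min, so the 1.5 s is most naturally the gap between tones.

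**4. Rejection rate with equal trials.** Simulated paired t-tests with n = 36, N = 200 in both recordings and 1–20 independent bins averaged rejected in 0.034–0.059 of runs at a nominal 0.05.

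**5. Unequal trials.** The floor shifts by sqrt(pi/(4·N2)) − sqrt(pi/(4·N1)):

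- 200 versus 160: +0.007
- 200 versus 140: +0.012
- 200 versus 120: +0.018

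As an illustration, suppose every post-dose recording kept 140 of 200 trials. The SD of the difference is sqrt(0.033² + 0.039²) = 0.051, so d = 0.0122/0.051 = 0.24. With n = 36, rejection is about 0.29 for one bin. Averaging four independent bins doubles d to 0.48 and gives about 0.80. There is no neural effect in either case. The plan has neither a rule for matching counts nor an N-corrected phase measure.

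**The case against.** The strongest reply is that the confirmatory test may never use pre-stimulus ITC. Section 5.6, the synopsis analysis plan and Section 5.7 all speak of post-stimulus gamma, and the abstract ties synchrony to the evoked response. The tag in 5.4 follows a joint list and may mean power before the tone and evoked measures after it. The synopsis also labels the study exploratory for MEG. This stands in part: it limits the consequence and shows that the sections conflict. It does not remove the endpoint, because Section 5.6.2 attaches the tag directly to inter-trial coherence and 5.4 calls the measure primary.

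Three stronger readings are tempting, and the documents do not support them.

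- **That the post-stimulus ITC endpoint is weakened by the company it keeps.** Sections 5.6 and 5.6.2 give each dependent measure its own ANOVA, with no composite and no stated alpha sharing. The extra measure takes neither signal nor alpha from the post-stimulus one.
- **That a specific family-wise error follows from counting hemispheres and tasks.** That needs independence between them, pure-tone jitter that is not stated, and one paired test per measure where the plan has a dose ANOVA with two contrasts.
- **That power equals alpha for every possible drug effect.** No pre-stimulus ITC window is defined. Bins within about 25–40 ms of onset can pick up the evoked response, and unequal trial counts move the floor.

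The criticism does not reach pre-stimulus gamma total power, which is a valid measure and fits the background findings in Section 1.3.

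**Conclusion.** The point holds in limited form. Well before tone onset, ITC as defined in Section 5.2 is a function of trial count alone (0.063 at 200 trials). It cannot show a drug effect on pre-stimulus synchrony. With equal counts, a test on it away from onset rejects at about its nominal 5%. Departures from the floor come from filter leakage near onset or from unequal usable trials.

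For the steady-state task this is well supported. It rests on the silent gap and does not need a particular jitter width; it assumes that gamma locked to the previous tone does not persist across that gap. For the pure-tone task, the interval, jitter and trial count are not given. There the conclusion rests on the protocol's own treatment of -400 to -100 ms as background, and the floor would be 0.089–0.125 if 50–100 trials are assumed.

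The practical weight depends on which section governs. Under 5.4 and 5.6.2, an uninformative measure is primary; under 5.6, it is not. That disagreement needs resolving in its own right. The post-stimulus ITC endpoint itself is not called into question.

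**What to change.** 1. In Sections 5.2, 5.4 and 5.6.2 and the synopsis efficacy list, reword the gamma endpoint as: *gamma total power (pre- and post-stimulus) and inter-trial coherence (post-stimulus only)*, and define the post-stimulus window.
2. Keep pre-stimulus ITC only as a check that each recording sits at its expected chance floor.
3. Reconcile 5.4 and 5.6.2 with 5.6, the synopsis analysis plan and 5.7 so that all name the same primary gamma measures. State whether pre-stimulus total power is primary or secondary; the rewording in step 1 does not settle this.
4. For the ITC that remains, equalise trial counts between the recordings being compared or use an N-corrected phase measure, since the formula in 5.2 has no correction for N.

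The cost is a short wording change in four places and one decision about the primary gamma set. Step 4 adds one line to the analysis specification. No new data are needed, and no test that could inform on the drug is lost.
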